13.9 Additional Follow Ups

Additional Visits

Patients will receive brief (30min) telephone calls in the months that do not include in person visits (in months 3, 5, 7, 9, and 11 after the procedure). These counseling sessions are primarily designed to improve adherence to recommendations to consume a healthy diet and increase physical activity to promote weight loss and overall health.

Additional In Person Visits

In addition to the visits above, patients will visit the clinic in 4, 8 and 10 months after the procedures. In these visits, patients will meet with dietitians/nutritionists where he/she will be queried regarding their adherence to the post-procedure diet protocol and reminded to follow the instructions. These counseling sessions are primarily designed to improve adherence to recommendations to consume a healthy diet and increase physical activity to promote weight loss and overall health.

Before a patient is considered “lost to follow-up”, there must be at least three (3) documented attempts to contact the patients.

	
Title: Evaluation of EndoZip™ System (AS) in Obese Patients who failed to reduce weight with non-surgical weight-loss methods
		
Document No: CL00003	Rev: 1.0	Page: 48 of 83	

13.10 Schedule of Events

Parameters	Screening	Visit 1	Visit 2	Visit 3	Visit 4	Visit 5	Visit 6	Visit 7	Additional In-Person Vits
		Procedure Day (30 days after ICF)	1 week (7-10 days) after the discharge	1 month ($\pm 1\text{wk}$) after the procedure	2 months ($\pm 1\text{wk}$) after the procedure	6 months ($\pm 1\text{wk}$) after the procedure	12 months ($\pm 1\text{wk}$) after the procedure	At 4,8,10 months after the procedure	
Informed consent	x								
Eligibility criteria	x								
Demographic data	x								
Medical history & concomitant medication	x		x	x	x	x	x	x	
Diet & physical activity adherence		x	x	x	x	x	x	x	x

	Title: Evaluation of EndoZip™ System (AS) in Obese Patients who failed to reduce weight with non-surgical weight-loss methods	
	Document No: CL00003	Rev: 1.0
		Page: 49 of 83

Parameters	Visit 1	Visit 2	Visit 3	Visit 4	Visit 5	Visit 6	Visit 7	Additional In-Person Vits
	Screening	Procedure Day (30 days after ICF)	1 week (7-10 days) after the discharge	1 month ($\pm 1\text{wk}$) after the procedure	2 months ($\pm 1\text{wk}$) after the procedure	6 months ($\pm 1\text{wk}$) after the procedure	12 months ($\pm 1\text{wk}$) after the procedure	At 4,8,10 months after the procedure
Weight, Height, Waist circumference	x	x	x	x	x	x	x	x
Physical examination and Vital signs	x	x	x	x	x	x	x	x
Laboratory tests	x				x	x	x	
Electrocardiogram (ECG) test		x						
Gastric Emptying Breath Test (GEBT)	x					x		

	
Title: Evaluation of EndoZip™ System (AS) in Obese Patients who failed to reduce weight with non-surgical weight-loss methods 
		
Document No: CL00003	Rev: 1.0	Page: 50 of 83	

Parameters	Visit 1	Visit 2	Visit 3	Visit 4	Visit 5	Visit 6	Visit 7	Additional In-Person Vits
	Screening	Procedure Day (30 days after ICF)	1 week (7-10 days) after the discharge	1 month ($\pm 1\text{wk}$) after the procedure	2 months ($\pm 1\text{wk}$) after the procedure	6 months ($\pm 1\text{wk}$) after the procedure	12 months ($\pm 1\text{wk}$) after the procedure	At 4,8,10 months after the procedure
Pregnancy Test		x						
Quality of life questionnaire (IWQOL)	x				x	x	x	
Psychological health questionnaire (PHQ-9)	x							
Sleep Apnea test (HSTs)	x				x	x	x	
EndoZip™ Procedure		x						

	Title: Evaluation of EndoZip™ System (AS) in Obese Patients who failed to reduce weight with non-surgical weight-loss methods		
Document No: CL00003	Rev: 1.0	Page: 51 of 83	

Parameters	Visit 1	Visit 2	Visit 3	Visit 4	Visit 5	Visit 6	Visit 7	Additional In-Person Vits
	Screening	Procedure Day (30 days after ICF)	1 week (7-10 days) after the discharge	1 month ($\pm 1\text{wk}$) after the procedure	2 months ($\pm 1\text{wk}$) after the procedure	6 months ($\pm 1\text{wk}$) after the procedure	12 months ($\pm 1\text{wk}$) after the procedure	At 4,8,10 months after the procedure
Usability Questionnaire		x						
Endoscopy Procedure		x			x	x		
AEs and SAEs ¹		x	x	x	x	x	x	x

¹ Adverse events will be monitored continuously until the end of the study period. AEs that are still unresolved at the last study visit will be followed for outcome information until resolution or stabilization of the event for a continuous period of 2 weeks, whichever occurs first. Unresolved SAEs will be followed until resolved.

	Title: Evaluation of EndoZip™ System (AS) in Obese Patients who failed to reduce weight with non-surgical weight-loss methods		
Document No: CL00003	Rev: 1.0	Page:	52 of 83

13.11 Required Concomitant Medications or Therapies

13.11.1 Concomitant Medications, Treatments, and Procedure

All concomitant prescription medications taken by the patient will be recorded as prior medications during screening and concomitant medications taken during study participation will be recorded on the electronic case report forms (eCRFs). Assessment of eligibility will include a review of permitted and prohibited medications. For details, refer to eligibility criteria.

For this protocol, a prescription medication is defined as a medication that can be prescribed only by a properly authorized/licensed clinician. Medications to be reported in the eCRF are concomitant prescription medications, over-the-counter medications and non-prescription medications.

13.11.2 Reduce Medications, Treatments, and Procedure

Use of non-investigational medicinal products

Prophylactic topical and/or systemic antibiotic agents may be prescribed by Investigators, as rescue (or escape) medication to alleviate the anticipated adverse reactions. This may be done per recommendations in the post-procedural guidance, i.e. the post-procedural protocol used by the multidisciplinary team, or per routine local practice. NOTE: Such medication will be recorded as a concomitant medication in the appropriate study eCRF. Dose, duration and frequency will be in accordance with local practice. No special arrangements for the prescribing practices are provided in this protocol. These medicinal products do not fall within the definition of investigational medicinal products in Directive 2001/20/EC and can be referred to as NIMPs.

14.0 Statistical Analysis

14.1 Sample Size Determination

This is a pilot study that will include up to 45 patients; no statistical considerations were made to determine the sample size.

The first two (2) patients per site will be considered as run-in period, to compensate for any learning curve that may be required for the EndoZip performance evaluation.

Safety evaluation will include all enrolled patients.

	Title: Evaluation of EndoZip™ System (AS) in Obese Patients who failed to reduce weight with non-surgical weight-loss methods		
Document No: CL00003	Rev: 1.0	Page:	53 of 83

14.2 Description of statistical methods

14.2.1 Analysis of Populations

Full Analysis Set (FA): includes all enrolled patients who undergone EndoZip procedure, excluding patients who enrolled in the run-in period.

Modified Full Analysis Set (mFA): The modified full (mFA) analysis set will include all patients who have at least one post initiation follow up visit and met the study Eligibility Criteria, and enrolled after the run-in period.

Per-Protocol (PP) analysis set: includes all patients from the mFA set who do not have any major protocol violations, and enrolled after the run-in period, and enrolled after the run-in period.

Statistical Analysis of Analysis Sets: Safety assessments will be performed on all enrolled patients set.

The mFA will serve as the principal data analysis set for the primary and secondary statistical efficacy endpoints. The primary, secondary efficacy assessment will also be performed on the PP and FA cohorts for descriptive purposes and to show consistency of study results.

14.2.2 General Methods:

Statistical analyses will be mainly descriptive in nature. Any statistical tests if performed will be two-sided, unless otherwise stated.

Study data will be summarized with descriptive statistics and presented in tables and figures. Continuous variables will be summarized by a mean, standard deviation, minimum, median and maximum and categorical variables by a count and percentage. If multiple measurements are taken in a single patient, statistics described below will be appropriately modified to accommodate the within patient correlation.

Any deviation from specified statistical plan will be in addition to “per protocol” analysis and will be reported as such Post-hoc analysis will be conducted according to the existing data gathered, if necessary.

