7.0 Benefit - Risk Assessment

7.1 Potential Benefits

EndoZip™ System is an automatic, operator-friendly ESD that allows the user to create multiple internal gastric segmentation in the stomach by using an endoscopic approach. The System generates an endoluminal gastroplasty that restricts the stomach and impair motility. Since this is an endoluminal approach, the potential for leaks has been significantly minimized. Also, this procedure is reversible and requires short recovery duration, and thus may be applied to a much wider patient population, by gastroenterologists as well as surgeons.

NiTiNotes has performed several preclinical and clinical studies in the development process with prototypes of varying designs as with the final device configuration.

In a First In Human study including 11 patients and 31 suture procedures, the first EndoZip prototype device presented promising safety and effectiveness results of %TBWL of 16.2 ± 6.0 at 6 months. No SAE related to the study occurred within the study duration. In an extended feasibility study a technical failure occurred and study was early terminated. The final design configuration includes improvements aim to minimize the likelihood of such an event.

The following are potential benefits of the EndoZip™ System stratified by key stakeholders:

Physicians:

- An effective non-surgical, long lasting treatment.
- Facilitate reduction in comorbidities.
- User-friendly procedure that has a minimal learning curve and provides reproducible results (not operator-dependent).
- Can be readily available for in clinic use, thereby improving patient access.
- Lower risk profile while still providing clinically significant weight loss outcomes.
- Short procedure with potential of cost reduction.

	Title: Evaluation of EndoZip™ System (AS) in Obese Patients who failed to reduce weight with non-surgical weight-loss methods		
Document No: CL00003	Rev: 1.0	Page:	30 of 83

Patients:

- Favorable safety profile with minimal trauma.
- Effective non-surgical, long lasting treatment.
- Potentially easier and shorter recovery.

Healthcare System:

- Lower expenditure - Patients are expected shorter recovery and reduced complications
- Procedure can be conducted by endoscopists and surgeons

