8.0 Study Objectives

8.1 Primary objectives

The evaluate the safety and effectiveness of the EndoZip system procedure, followed by lifestyle modifications, for weight reduction in obese patients with BMI of 30-40 kg/m².

8.2 Secondary objectives:

- To evaluate the potential improvement in patients' conditions.
- To evaluate the duration related to the EndoZip procedure.
- To evaluate physicians' satisfaction related to the EndoZip usability.

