9.2 Secondary endpoints

The following secondary endpoints will be evaluated:

1. Percent of excessive weight loss (%EWL) over 6 and 12 months.
2. Reduction of weight and waist circumference over 6 and 12 months.
3. Impact of EndoZip procedure on gastric motility at 6 months.
4. Changes in Weight-related Quality of Life (IWQOL) Questionnaire scores at 6 and 12 months.
5. Time analysis including procedure duration, anesthesia duration, patient recovery duration.
6. Change in comorbid conditions over 12 months evaluated by:
 - a. Blood pressure
 - b. Glucose, HbA1c
 - c. Lipid levels (Total Cholesterol, LDL-C, HDL-C, and triglycerides)
 - d. Sleep Apnea test
7. Physicians' satisfaction based on a questionnaire

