10.0 Study Design

[figure not shown]
This multicenter, prospective, single arm study will include up to 45 patients (10-20 patients per site), aimed at evaluating the performance of the EndoZip System in obese patients who failed to reduce weight with non-surgical weight-loss methods.

The first two (2) patients in each site will be considered as run-in period, to compensate for any learning curve that may be required for the EndoZip performance evaluation.

Patients will be enrolled at up to 5 clinical sites in Europe and Israel. Patients who meet the eligibility criteria is expected to come the clinic for at least 10 visits.

	
Title: Evaluation of EndoZip™ System (AS) in Obese Patients who failed to reduce weight with non-surgical weight-loss methods
	
Document No: CL00003	Rev: 1.0	Page: 33 of 83

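### Under Section 14.2.1 every efficacy set drops each site's first two cases, and no other set is named for procedure time and usability, so their planned summaries may omit the earliest uses of the device

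*Combined protocol and SAP*

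**What the plan says.** Section 10.0 sets up the run-in: "The first two (2) patients in each site will be considered as run-in period, to compensate for any learning curve". Section 14.1 repeats it.

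Section 14.2.1 then defines three sets. FA is the treated patients without the run-in. mFA adds a follow-up visit and confirmed eligibility, again without the run-in. PP is the part of mFA free of major violations. On their use it states: "The mFA will serve as the principal data analysis set for the primary and secondary statistical efficacy endpoints". PP and FA serve as support. Within Section 14, only safety is assigned to all enrolled patients.

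Section 8.2 gives three secondary objectives. One is "To evaluate the duration related to the EndoZip procedure" and another is physicians' satisfaction with usability. In Section 9.2 they become endpoints 5 ("Time analysis including procedure duration, anesthesia duration, patient recovery duration") and 7. Section 14.6 plans descriptive statistics with 95% confidence intervals for both and names no analysis set.

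Section 7.1 lists among the benefits for physicians: "User-friendly procedure that has a minimal learning curve and provides reproducible results (not operator-dependent".

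The synopsis (Analysis Populations) excludes the run-in from FA but states no such exclusion for mFA, or for PP, which is drawn from mFA.

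**The concern.** Leaving out the first cases at each site can be defended for 12-month weight loss, where the aim is to describe the effect once the operator is familiar with the device. It fits procedure time and ease of use less well, because the early cases are part of what those objectives ask about. Appendix B asks whether the physician would need technical support and whether the instructions for use are sufficient. Those answers matter most for a new user.

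Two further conditions of the mFA, a follow-up visit and confirmed eligibility, have no bearing on how long a procedure took or how the device handled.

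At stake is the representativeness of two stated secondary objectives. If early cases are slower or harder, the reported times will be shorter and the scores better than a new site would meet. No planned table would show the difference.

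**Working it through.** **Which set applies.** The plan gives no figure to reproduce here, so the texts are set side by side first.

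| Set | Section 14.2.1 | Synopsis |
|---|---|---|
| FA | run-in excluded | run-in excluded |
| mFA | run-in excluded | no exclusion stated |
| PP | run-in excluded | drawn from mFA, no exclusion stated |

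The Section 14.2.1 rule is worded for efficacy endpoints. There are two readings:

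- Time and usability count as secondary efficacy endpoints. Under Section 14.2.1 they are then summarised on mFA, PP and FA, all without the run-in.
- They do not count as efficacy endpoints. The plan then assigns them no set at all.

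Either way the text needs a statement. No analysis by case order, by operator, or of run-in against later cases appears in Section 14.

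**How many cases.** Inputs: up to 45 patients and two run-in patients per site (Section 14.1); 10 to 20 patients per site and up to five sites (Section 10.0); three named centres (synopsis).

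- Three sites: 2 × 3 = 6; 6/45 = 13.3%; 39 remain.
- Four sites: 2 × 4 = 8; 8/45 = 17.8%; 37 remain.
- Five sites at the Section 10.0 minimum need 5 × 10 = 50 patients, above the cap of 45. Four sites need 4 × 10 = 40, which fits. Four is therefore the most that Section 10.0 allows at 45 patients.

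**Effect on a mean time.** Let later cases average m and run-in cases average m(1 + e), with run-in share p. The mean over all cases is m(1 + p·e), so it exceeds the reported mean m by p·e.

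| Assumed excess e | Three sites (p = 13.3%) | Four sites (p = 17.8%) |
|---|---|---|
| 50% | 0.5 × 13.3% = 6.7% | 0.5 × 17.8% = 8.9% |
| 100% | 13.3% | 17.8% |

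The documents give no procedure times, so e is purely an assumption. If e is zero there is no shift.

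**Precision.** The approximate 95% half-width for a mean is 1.96/√n in SD units: 0.314 for n = 39, 0.322 for n = 37 and 0.292 for n = 45. The gain from adding the run-in cases is small. The issue is which cases are represented.

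**What the run-in cases could show.** The difference detectable with 80% power (two-sided 5%, normal approximation, cases taken as independent) is (1.96 + 0.84) × √(1/r + 1/k) SD, for r run-in and k later cases. It is 1.23 SD for 6 against 39 and 1.09 SD for 8 against 37. Only a large early effect would stand out, so a descriptive display is the right ambition.

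**The case against.** The strongest reply is that this is a descriptive single-arm pilot with an openly declared run-in, and that describing performance after a short familiarisation is a legitimate choice. That stands for weight loss. It does not settle the set for two objectives that concern the procedure itself.

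The other side is also right to limit several stronger readings that a reader might infer:

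- *Time and usability are analysed only in sets without the run-in.* This is true of Section 14.2.1 if the efficacy rule covers them. The wording leaves that open, and the synopsis mFA states no exclusion.
- *The trial cannot examine early learning.* The usability questionnaire is completed on the procedure day with no run-in exemption, Section 14.2.2 permits post-hoc analysis, and cases from the third onward remain in the sets. The plan does not schedule the comparison, but it does not prevent it. A table chosen after the results are seen would, however, carry less weight than a prespecified one.
- *The trial tests ease of use or a minimal learning curve.* The summaries are descriptive, and the learning-curve statement is a listed benefit, neither an objective nor an endpoint.
- *Up to 22.2% of cases (10 of 45) are lost with five sites.* Section 10.0 says "Patients will be enrolled at up to 5 clinical sites in Europe and Israel", and the synopsis gives only an upper limit of 20 per site. The minimum of 10 per site in Section 10.0 rules out five sites at 45 patients.
- *Run-in cases are every operator's first contact with the device.* One named centre ran the earlier prototype study (31 procedures in 11 patients), and Section 13.3 asks for experience with endoscopic suturing devices and sponsor training. Any early excess may therefore be small.

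The complaint about follow-up and eligibility conditions applies to mFA and PP. FA in Section 14.2.1 carries neither.

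**Conclusion.** The point holds as a gap in specification with a possible favourable bias. In Section 14.2.1 every efficacy set omits the first two patients per site, and Section 14.6 gives procedure time and usability no other set. The synopsis and Section 14.2.1 also disagree on the mFA.

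If the Section 14.2.1 rule is followed, 13.3% (three sites) to 17.8% (four sites) of 45 cases drop out of these summaries, before any other exclusion. An assumed 50% excess in run-in time would put the all-case mean 6.7% to 8.9% above the reported one. The direction and size rest on that assumption, and the documents neither support nor contradict it.

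The primary weight-loss endpoints are not affected. A worthwhile and inexpensive improvement, not a threat to the trial's main conclusions.

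**What to change.** 1. In Sections 14.2.1 and 14.6, state that procedure, anaesthesia and recovery times and the usability questionnaire are summarised on all patients in whom the EndoZip procedure was started, run-in included, with no follow-up-visit or eligibility condition.
2. Show run-in and later cases side by side, by case order within operator where possible. Keep this descriptive.
3. Keep the run-in exclusion for the weight-loss endpoints.
4. Reconcile the mFA definition in the synopsis with that in Section 14.2.1.

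The cost is a few lines of SAP text, two table columns and possibly slightly less favourable times and scores. The questionnaire is already scheduled for every procedure day. The schedule of events has no row for the times and Section 13.3 refers only to relevant data, so confirm that the eCRF captures all three durations for run-in patients too.

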14.2.3 Handling of the Type I Error

The overall significance level for this study is 5%, confidence intervals will be two-sided using a 95% confidence level, except for treatment by site interaction that will be tested at a significance level of 10%.

	Title: Evaluation of EndoZip™ System (AS) in Obese Patients who failed to reduce weight with non-surgical weight-loss methods		
Document No: CL00003	Rev: 1.0	Page:	54 of 83

14.3 Demographic, Medical history, and Baseline characteristics

Basic demographic and baseline characteristics will be collected during the screening visit. In addition to the evaluation of the patient's medical history in terms of study eligibility, all relevant medical conditions will be documented on the appropriate eCRF.

The patient's entire obesity history will be collected on the appropriate eCRF including previous treatments, medications and interventions done to lose weight.

Events that occur after signing of informed consent but prior to the Endozip™ procedure, unless serious and due to protocol – mandated procedure, should be recorded on the Medical History eCRF.

14.4 Primary Endpoint Analysis

The %TBWL at each visit will be calculated as $100 * (\text{Weight(BL)} - \text{Weight(Visit)}) / \text{Weight(BL)}$, where weight is measured in kilograms. %TBWL will be summarized with descriptive statistics at each follow-up visit.

%TBWL will be evaluated by using repeated measures analysis of covariance (ANCOVA MIXED model). Baseline weight, center and visit will be used as covariates. Baseline weight will be entered as a continuous variable so that the potential for co-linearity problems will be minimized.

The unstructured covariance matrix structure will be used. If the model doesn't converge, then either the compound symmetry or autoregressive (whichever model has the lower AIC statistic) covariance matrix structure will be used instead. For this evaluation no imputation of missing data is considered beyond the model estimates.

The model estimated mean %TBWL at each visit will be presented with 95% confidence interval and level of significance.

A count and percentage of patients achieving at least 5% TBWL will be presented with exact 95% confidence interval.

14.4.1 Subset Analysis of the primary endpoint:

Additionally, the %TBWL median, mean and standard deviation and percent of patients with greater than 5%TBWL will be summarized. Covariates may include demographic data (sex, age, BMI) or other baseline characteristics.

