3.0 Protocol Synopsis

Protocol Number	CL00003
Protocol Title	Evaluation of EndoZip™ System (AS) in Obese Patients who failed to reduce weight with non-surgical weight-loss methods
Study Sponsor	
NiTINotes, [name]
 
[contact]
 
[contact]

Sponsor Representative	
[name] VP QA, Regulatory and Medical Affairs

Study Type	Pilot study
Study Product	EndoZip™ System (AS)
Study Location	Europe, Israel
Study Centers	
 1. Hospital Universitario HM Sanchinarro, Madrid, SPAIN 2. Fondazione Policlinico Universitario Agostino Gemelli IRCCS (CERTT), Rome, Italy 3. Rabin Medical Center, Petah Tikva, Israel

	
Title: Evaluation of EndoZip™ System (AS) in Obese Patients who failed to reduce weight with non-surgical weight-loss methods
	
Document No: CL00003	Rev: 1.0	Page: 9 of 83

Investigators	
 1. [name] 2. [name] 3. [name]
Study Duration	The duration for each participant will be 12 months; the total study duration is expected to be approx. 18 months
Study Design	The study is planned as a multicenter, prospective, single-arm, open-label, controlled clinical trial.
Planned Visits	
 • Office visits: 1 week, and 1, 2, 4, 6, 8, 10, and 12 month(s) • Remote follow up (by Phone): 3, 5, 7, 9, and 11 month(s) • Endoscopy follow up: 2 and 6 months • Motility evaluation by Gastric Emptying Breath Test (GEBT): 6 months • Physical examination, vital signs, waist circumference and BMI: 1 week, 1, 2, 4, 6, 8, 10 and 12 months • Blood tests: 2, 6 and 12 months • IWQOL-Lite: 2, 6 and 12 months • Sleep Apnea (only for the relevant population): 2, 6 and 12 months
Patient Population	Male and Female with obesity, BMI of 30-40 kg/m ² , between the ages of 21 and 70 who failed to reduce weight with non-surgical weight-loss methods
Planned # of Patients	Up to 45 patients
Planned # of Sites	Up to 5 clinical sites
Planned # of Patients per Site	Up to 20

	Title: Evaluation of EndoZip™ System (AS) in Obese Patients who failed to reduce weight with non-surgical weight-loss methods	
Document No: CL00003	Rev: 1.0	Page: 10 of 83

Study Objective	
The objective of this study is to evaluate the safety and effectiveness of the EndoZip system procedure, coupled with lifestyle modifications, for weight reduction in obese patients with BMI of 30-40 kg/m².

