6.3 Clinical data to Date

One clinical study has been conducted to date. The study was designed to evaluate the safety and the outcomes of the EndoZip prototype system with respect to obese patients' weight loss in 6 months. It was a single arm, prospective single center study, conducted by [name] at the Bariatric Endoscopy unit of HM Sanchinarro University Hospital, Madrid, Spain. The institutional review board approved the study. The study was conducted in accordance with the ethical principles detailed in the

	Title: Evaluation of EndoZip™ System (AS) in Obese Patients who failed to reduce weight with non-surgical weight-loss methods		
Document No: CL00003	Rev: 1.0	Page:	28 of 83

Declaration of Helsinki and was consistent with Good Clinical Practices recommendation (Clinicaltrials.gov, NCT03472196). The study results were published on January 2020 at Obesity Surgery Journal [OBES SURG (2020) 30:1696–1703].

Study Design - Patients in this study were instructed to be on a liquid diet and fast a day prior the procedure. BMI, waist circumference, blood tests and a Quality of life questionnaire were recorded prior the procedure.

Patients were followed up 7-10 days, 6 weeks, 3 and 6 months after the procedure. In the follow up visits, changes in the patients' well-being, blood tests outcomes, compliance with the diet instructions and weight were recorded. At 6 weeks, 3 and 6 months after the procedure, presence and location of the stiches by means of endoscopy, and quality of life were recorded.

Results - Eleven obese class I and II patients are included in this analysis.

The age range of the patients was 35-51 years, their average weight was 111.1 kg, their average height was 174 cm and their BMI (kg/m²) ranged from 30.2-39.7.

Thirty-one (31) procedures were applied in 11 patients. All procedures (100%; 95% CI [89%,100%]) were completed successfully.

All eleven patients reached 3-months and adhered until 6-month follow-up. The mean \pm SD TBWL at 3-month and 6-month was 14.8 ± 4.8 Kg and 17.8 ± 6.7 Kg, respectively (p<0.001). The mean \pm SD %TBWL at 3-month and 6-month was $13.5 \pm 4.7\%$ and $16.2 \pm 6.0\%$, and the mean \pm SD %EBWL was $46.5 \pm 28.6\%$ and $54.3 \pm 28.4\%$, respectively.

The mean \pm SD of waist circumference at baseline was 117 ± 9.4 and significantly (p<0.001) reduced 6 months after the EndoZip procedure to mean \pm SD of 100 ± 12.7 .

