12.3 Body Height, Weight and Waist Circumference

Height, Weight and Waist Circumference will be measured at all in-person visits. The results will be documented in the eCRF.

Waist Circumference Measuring instructions:

	Title: Evaluation of EndoZip™ System (AS) in Obese Patients who failed to reduce weight with non-surgical weight-loss methods		
Document No: CL00003	Rev: 1.0	Page:	38 of 83

To measure the waist, place a flexible tape measure between your bottom rib and your hip bone. The tape measure should be approximately in line with your belly button.

Take your waist measurement on a normal breath out

Don't pull or tuck in your stomach

Ensure the tape measure is level at the front and the back of your body

The tension of the tape should be such that the tape is held against the skin but not so tight as to cause an indentation in the skin

Waist Girth and Health Risk		
	Men	Women
Normal	78-94cm	64-80cm
Overweight (Elevated Risk)	94-102cm	80-88cm
Obese (High Risk)	>102cm	>88cm

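### The fallback covariance structures fit one variance to all visits, so if the unstructured model fails, the 12-month CI for mean %TBWL is too narrow when the SD is still rising

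*Combined protocol and SAP*

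**What the plan says.** Section 14.4, repeated in the synopsis under Primary Endpoints, fits a repeated-measures model to %TBWL with baseline weight, center and visit. The covariance is unstructured. On non-convergence, "either the compound symmetry or autoregressive (whichever model has the lower AIC statistic) covariance matrix structure will be used instead". No heterogeneous-variance version and no robust standard error is named. The model mean at each visit is reported with a 95% CI and a significance level. At 12 months that mean is the first co-primary endpoint (section 9.1).

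Weight data are frequent. Section 12.3 states: "Height, Weight and Waist Circumference will be measured at all in-person visits". The synopsis schedule gives eight such visits after the procedure, from 1 week to 12 months. Section 14.4 does not list which visits enter the model.

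On size, section 10.0 says the study "will include up to 45 patients (10-20 patients per site"). It adds: "The first two (2) patients in each site will be considered as run-in period". Section 14.2.1 leaves the run-in patients out of the efficacy sets.

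**The concern.** An unstructured covariance gives each visit its own variance. Compound symmetry and first-order autoregressive, in ordinary form, do not: one variance serves week 1 and month 12 alike. Choosing between them by AIC settles the correlation pattern, not the variance pattern.

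Percent weight loss starts at zero for everyone, so its spread at week 1 and month 1 is likely to be small. Those visits pull the pooled SD down. If the 12-month SD is well above the pooled value, the fallback understates the standard error at the visit that matters, and the CI for mean %TBWL claims more precision than the data support. The primary unstructured model is sound; the point concerns only the written contingency.

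**Working it through.** The plan states no precision or coverage figure, so there is nothing to reproduce first.

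**Inputs from the documents**
- Post-procedure weight visits: 0.25 (1 week), 1, 2, 4, 6, 8, 10 and 12 months. An unstructured matrix then has 8 × 9 / 2 = 36 parameters.
- SD of %TBWL: 4.7 at 3 months and 6.0 at 6 months, n = 11 (section 6.3).
- Patients after run-in: 3 listed sites × 10 − 6 = 24; 45 − 2 × 3 = 39; 45 − 2 × 5 = 35.

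**Assumed SD paths.** A power curve through the two known SDs has exponent ln(6.0/4.7)/ln 2 = 0.352. It gives 1.96, 3.19, 4.07, 5.20 and 6.00 at 0.25, 1, 2, 4 and 6 months. After month 6 the SD either stays on the curve (rising), stays at 6.0 (plateau), or falls in a straight line.

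**Large-sample coverage.** With complete data, compound symmetry fits the pooled SD, the root mean square over the visits. The coverage of the nominal 95% CI at 12 months is 2Φ(1.96 × pooled SD / 12-month SD) − 1.

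| Path after month 6 | 12-month SD | Pooled SD | Ratio | Coverage |
|---|---|---|---|---|
| Rising | 7.66 | 5.57 | 0.727 | 84.6% |
| Plateau | 6.00 | 5.02 | 0.837 | 89.9% |
| Falling to 4.5 | 4.50 | 4.60 | 1.022 | 95.5% |
| Falling to 4.0 | 4.00 | 4.47 | 1.118 | 97.2% |

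The break-even 12-month SD is 4.63 (4.58 to 4.73 if the week-1 SD is anywhere from 1.0 to 3.0). Coverage is 93% at an SD of 5.17 and 90% at 5.97. Using only the two documented SDs, without extrapolation, the pooled value is √((4.7² + 6.0²)/2) = 5.39, the ratio is 0.898 and coverage at the later visit is about 92%.

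**How often the fallback is used.** Simulated with REML, visit, three centers and baseline weight, autoregressive (0.9) or exchangeable (0.85) true correlation, and monotone dropout. The 15% and 30% dropout rates are assumptions. The solver was purpose-written, so commercial software may differ.
- n = 24: 2/2,000 failures with 15% dropout; 272/6,896 = 3.9% with 30%.
- n = 35: 0/1,000 with 15%; 2/1,000 with 30%.

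**Coverage in the failed trials** (n = 24, 30% dropout; ranges span two degrees-of-freedom rules)

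| Path | Failures | AIC fallback | Heterogeneous | Corrected sandwich |
|---|---|---|---|---|
| Rising | 120 of 3,448 | 92–96 covered: 77–80% | 111: 92.5% | 113: 94.2% |
| Plateau | 152 of 3,448 | 140–142 covered: 92–93% | 150: 98.7% | 147: 96.7% |

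The Monte Carlo SE of the fallback coverage is about 4 points (rising) and 2 points (plateau), so the plateau result is not clearly below 95%.

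**Fallback forced on every trial** (n = 24), to isolate the mechanism: rising 84–86%, plateau 87–90%, falling to 4.5 91–95%, falling to 4.0 94–97%. A separate simulation at n = 39 with 15% dropout gave 86%, 88% and 94% for the first three, and 96% with a constant SD. The constant-SD control shows that the shortfall comes from the single-variance restriction.

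**Overall loss** = failure rate × shortfall, at n = 24 with 30% dropout. Rising: 0.035 × (15.0 to 18.3) = 0.5 to 0.6 points. Plateau: 0.044 × (1.6 to 2.9) = about 0.1 point. At n = 35 it is close to zero.

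**The case against.** The strongest objection is that the fallback will hardly ever be used. A non-trivial failure rate needs both the smallest sample (24) and 30% dropout, and the only retention figure in the documents is 11 of 11 to 6 months. At n = 39 with 30% dropout, a further simulation had 0 failures in 150. This stands, and it is why the impact is minor. The forced-fallback figures show the mechanism, not the expected behaviour of the plan.

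The direction is also unproven. For 4.7 against 6.0 in 11 patients, a paired variance test gives p of about 0.12 to 0.42 for assumed correlations of 0.9 to 0.5. A falling SD makes the interval about right or somewhat wide. This stands too: a shortfall is clear only if the SD keeps rising after month 6. The break-even of 4.63 is a large-sample figure for compound symmetry. The simulated AIC fallback still covered only 91–95% at an SD of 4.5, so the break-even does not describe small samples exactly.

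The model may also use only the five numbered follow-up visits. That means 15 covariance parameters and fewer failures (2/600 at n = 24 with 30% dropout). But dropping months 4, 8 and 10 removes late visits and widens the variance gap. The pooled SD becomes 4.53 (plateau) or 5.00 (rising), and large-sample coverage about 86% or 80%. The objection lowers the frequency, not the conditional problem.

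Finally, no decision hangs on this interval. Section 14.2.2 says: "Statistical analyses will be mainly descriptive in nature". There is no threshold for mean %TBWL, raw SDs are tabulated at each visit, and the exact CI for the responder percentage is untouched. In failed plateau trials the mean half-width moves only from 2.28 to about 2.77 points (heterogeneous structures). All of this limits the stakes; none of it makes the written fallback the better choice.

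**Conclusion.** The concern holds in its conditional form: if the unstructured model fails, the ordinary structures are used, and the 12-month SD exceeds the pooled SD, the 12-month CI for mean %TBWL is too narrow. In failed trials at n = 24 with 30% dropout, coverage was 77–80% with a rising SD and 92–93% with a plateau. Averaged over all trials in that setting, the loss is at most about 0.6 points.

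The size rests on assumed SD paths beyond the two documented values, assumed dropout, and eight visits in the model. Confidence is medium. This is a cheap improvement, not a defect in the main analysis.

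**What to change.** In section 14.4 and in the synopsis, replace the fallback sentence with a rule of this content: *on non-convergence, use heterogeneous compound symmetry or heterogeneous first-order autoregressive, taking the one with the lower AIC; if neither converges, use the ordinary compound symmetry or autoregressive structure with a small-sample-corrected empirical (sandwich) standard error.*

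The cost is one sentence in two places and standard software options. Nothing changes if the unstructured model converges. In the simulated failures at least one heterogeneous structure converged in 272 of 272.

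The price is a wider interval when the fallback is used. Mean widths in the failed trials were:
- Plateau: 4.56 (current fallback), 5.53 (heterogeneous, +21%), 6.07 (sandwich, +33%).
- Rising: 5.08, 7.04 (+39%), 7.73 (+52%).

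In the rising case that extra width brings coverage close to 95%. In the plateau case the heterogeneous interval is somewhat conservative.
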